The products of Aim 1 will be: (1) a comprehensive taxonomy of types and features of telemedicine offered in response to the COVID-19 pandemic; (2) a nuanced understanding of the perspectives of those seeking to use telemedicine, including advantages and disadvantages, facilitators and barriers, and perceived value; and (3) stakeholder-informed input for use in Aim 2 analyses, including details of site characteristics and telemedicine interventions as well as outcomes prioritized by stakeholders.

Data Sources

This will be a primary data collection using telephone interviews, for which participants will receive a stipend of \$40.

Data collection: For both patients and providers, semi-structured interview instruments will be designed to explore experiences with, advantages and disadvantages of, and barriers to and facilitators of telemedicine. The interview guides will be finalized with input from the Stakeholder Advisory Board and pilot tested for clarity. Trained interviewers will

PRINCIPAL INVESTIGATOR: [name]; [name]

conduct 30- to 45-minute individual interviews in English or Spanish. All interviews will be audio-recorded and professionally transcribed.

Confidentiality and Data Management: As stated in the PCORI Methodology Standards, researchers have an obligation to ensure confidentiality.⁶ All personally identifiable data will be redacted during transcription, and the code list linking transcripts to participant identity and consent forms will be stored separately and accessible only to the site PI. Audio recordings will be stored on protected servers accessible only to the site PI and team and will be destroyed after data analysis is complete.

Sample

We will recruit both patients and providers from primary care clinics that transitioned to telemedicine to ensure representation from individuals who have had experience with the technology. Both PCPs and patients will help us understand the features of telemedicine utilized (e.g. synchronous video, telephone calls) and their relative experiences with these features. Our approach to sampling PCPs from different practices and purposive patient sampling serves our goal of understanding telemedicine experience by diverse populations.

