For Aim 1A, we will use two sampling frames. First, we will survey one leader at each eligible adult primary care practice within the CRNs participating in Aim 2 (INSIGHT, OneFlorida, and STAR). The target sample size of practices is 250 practices. If our total sample size does not reach 250, or if we want to do targeted recruitment for specific practice types, we will draw additional primary care practices nationally using an Agency for Healthcare Research and Quality file of group practices.⁷

For Aim 1B, we will recruit PCPs from both sampling frames with experience using or attempting to use telemedicine, sampling for maximum variability across practice environments (e.g., high vs. low Medicaid patient share), locations (e.g., urban vs. rural), and clinical roles. We will recruit adult patients (English or Spanish speaking) with a chronic condition under study who have attempted to use or have used telemedicine. We will recruit patients through our participating CRNs, a patient registry at Mount Sinai (REMIND study (HS: 15-00792) and through provider nominations. We will conduct purposive sampling on the basis of age, primary language, insurance type, illness severity, and location. The target sample size is 75 patients and 25 providers.

In our inductive approach (see analysis section below), we will iteratively conduct interviews and analyze data until the team concurs that thematic saturation has been reached (when new interviews cease to yield new concepts).⁸ In addition, during the analysis, we will also critically assess our participant sampling selection to identify additional participants to interview to reflect specific perspectives or viewpoints. Although this means we cannot establish a precise sample size *a priori*, we conservatively plan for 25 PCPs and 75 patient interviews.

The advantage of using thematic saturation as a stopping criterion is that it allows us to avoid establishing a fixed sample size *a priori* in order to be able to respond flexibly to the data collection and analysis process.^{1,8} Using this approach, we plan to continue sampling and analyzing the data until we reach saturation. This means that we can increase the sample size of PCPs to more than 25 if we determine it is needed. (In addition, we can also increase or reduce the patient sample size, currently estimated at 75, if needed.)

Outcomes and Covariates

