Additionally, we will collect patient-reported outcomes (PROs) through REDCap surveys of 1,000 patients at Weill Cornell Medicine, delivered via the patient portal. The recruitment methods for this survey include, but are not limited to, the use of the Consent to be Contacted for Research (CCR) (WCM IRB protocol 1812019822; PI: [name]). For those patients who have opted into CCR participation and meet the inclusion criteria for this study, the study team will send recruitment message(s) via approved methods in accordance with CUIMC-NYP-WCM governance. By requesting CCR status for patients meeting study eligibility criteria, the study team agrees to contact only patients approved by the Institutional Review Board (IRB) for this specific study. The study team agrees to adhere to EpicTogether and the Tripartite processes. Contingent on the Tripartite committee(s)'s decision, all the relevant materials will be submitted in subsequent submissions to the IRB. The recruitment methods for patients who are approved to be contacted include, but not limited to, use of Epic's research recruitment message, phone call, email, and/or mail. The study team also agrees to maintain a record of patients contacted for, enrolled in, declined for, and withdrawn from the study, which the team will share at regular intervals with TRAC and the IRB. For patients who have not consented to be contacted for research, the study team will pursue the alternative methods of recruitment approved by the IRB office. Additional recruitment methods for the PRO survey include inviting patients who were recruited for the qualitative interviews, or patients who are nominated by their primary care providers. Invitations will be sent to patients via email, phone call and/or mail.

We will collect PROs on patient experiences based on the Patient Satisfaction Questionnaire (PSQ-18) (5-point subscale),²⁹ which includes patient satisfaction, communication quality with providers, and accessibility/convenience of care. For individuals who accessed a telemedicine visit, we will ask questions adapted from the validated Telemedicine Usability Questionnaire (TUQ), including the ease of use and access to the telemedicine service, quality of the interaction with the provider, and satisfaction.⁵ We will leverage stakeholder input and the Aim 1A survey to inform the duration of patient exposure to each of the three treatment arms.

Table 1

Measure	Data Source
PRIMARY OUTCOMES	

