Our sample sizes still provide sufficient power should we adopt a non-inferiority framework to test whether telemedicine visits are no less effective than in-person visits. For the ED visit outcome, if we assume that the minimum sample size is 25,000 in each of the three groups, and that between 20% and 5% of patients in the in-person arm have unplanned ED visits, we will have between 80% and 99% power to determine whether the telemedicine arm is no worse than 1 percentage point (absolute) lower than the in-person comparator. (This calculation was done with a z-test to determine a difference in proportions with a one-sided 2.5% significance level.) In fact, our study will have more power if the groups have more than 25,000 patients. For the patient satisfaction outcome, with 500 in each group, there will be 90% power with one-sided level of significance of 0.025 to determine if the decrease in mean level of patient satisfaction for the telemedicine group is no more than 0.2 standard deviations compared to the control group (in-person). We believe a 0.2 standard deviation effect size is reasonable for a non-inferiority margin because it lies below the 0.25 effect size that is typically deemed meaningful for patient satisfaction and quality of life instruments.

F. AIM 2 METHODS: DATA COLLECTION, MANAGEMENT, ANALYSIS

Data Collection Methods and Data Sources

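### The satisfaction survey admits Aim 1B interviewees, a route open to the telemedicine arms but not to in-person-only clinics, and no planned analysis accounts for recruitment route

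*Combined protocol and SAP*

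**What the plan says.** Section E (Aim 2 Methods, Outcomes) plans "REDCap surveys of 1,000 patients at Weill Cornell Medicine". The main route is the research-contact consent list, but the list of routes is open-ended. Two further routes are named: "inviting patients who were recruited for the qualitative interviews, or patients who are nominated by their primary care providers". No cap or nomination criterion is given for the second.

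Section C (Aim 1 Methods, Sample) fixes who the interviewees are. They are adults "with a chronic condition under study who have attempted to use or have used telemedicine". On clinics it says: "We will recruit both patients and providers from primary care clinics that transitioned to telemedicine". On numbers it says: "The target sample size is 75 patients and 25 providers", and it adds that the patient number may be raised or lowered. Interview patients come from the participating networks, a Mount Sinai registry and provider nominations.

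Table 1 lists PROs under primary outcomes. The Power Calculation compares satisfaction between arms, first as a difference and then, should a non-inferiority framework be adopted, against a 0.2 SD margin with 500 per group.

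**The concern.** Arms are defined by the clinic's model of care. Section E (Interventions and Comparators) gives the reason: patients who choose telemedicine are known to differ from those who do not. Recruiting survey respondents because they used or tried telemedicine brings that selection back for one of the outcomes listed as primary. These respondents will also already have spent 30 to 45 minutes discussing the advantages and barriers of telemedicine.

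Provider nominees raise a different question. The survey rates communication with the provider, and here the provider picks the respondent.

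If a route feeds some arms and not others, and its members differ in satisfaction from other respondents, the arm difference partly reflects how people entered the survey. That could create a difference, hide one, or tip a non-inferiority conclusion.

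**Working it through.** **Which arms each route can reach**

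- Interviewees: they must have telemedicine experience and come from clinics that transitioned to telemedicine. Telemedicine-only and telemedicine-supplemented clinics can supply them; in-person-only clinics should supply none.
- Nominees: any clinic in any arm can supply them. Nothing in the documents makes their share or their effect differ by arm.

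**Whether a planned analysis removes the problem**

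- The propensity score matching in section F (Primary Analysis) uses clinic-level characteristics. Recruitment route is not among them.
- The multiple imputation and likelihood methods for PRO data, and the check on whether missingness introduces selection bias, concern missing values rather than how a person entered the sample.
- No pre-pandemic PRO wave is described, so differencing is not shown to remove baseline differences in satisfaction.
- The log of patients contacted, enrolled, declined and withdrawn is kept for oversight reporting. It is not described as recording route or as an analysis variable.

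**The plan's own power figure**

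Inputs are 500 per group, a margin of 0.2 SD and one-sided 0.025 (Power Calculation). The standard error is √(2/500) = 0.0632 SD. Power = Φ(0.2/0.0632 − 1.96) = Φ(1.202) = 88.5%, close to the stated 90%; exactly 90% needs 526 per group.

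**Size of the shift**

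Shift in an arm's mean = (interviewees in the arm / arm size) × their difference in satisfaction from other respondents. The documents do not give that difference. I assume 0.25 to 0.5 SD; the lower end equals the effect size that the Power Calculation calls typically meaningful.

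| Interviewees in one arm | Arm size | Shift (SD) | Share of 0.2 SD margin |
|---|---|---|---|
| 75 (upper bound for the planned number) | 500 | 0.0375 to 0.075 | 19% to 38% |
| 75 | 333 | 0.056 to 0.113 | 28% to 56% |
| 19 | 500 | 0.0095 to 0.019 | 5% to 10% |
| 19 | 333 | 0.014 to 0.029 | 7% to 14% |

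The 19 is 75/4 = 18.75. It assumes an even split over the four health systems, with only Weill Cornell patients eligible for the survey. The 333 is 1,000 divided over three arms.

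**Effect on error rates (500 per group)**

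With bias b, two-sided type I error is Φ(b/0.0632 − 1.96) + Φ(−b/0.0632 − 1.96). If b favours telemedicine, false non-inferiority at a true deficit of 0.2 SD is Φ(b/0.0632 − 1.96). If b runs against telemedicine, non-inferiority power is Φ((0.2 − b)/0.0632 − 1.96).

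| Bias (SD) | Type I (nominal 5%) | False non-inferiority (nominal 2.5%) | Non-inferiority power if adverse (88.5% without bias) |
|---|---|---|---|
| 0.019 | 6.0% | 4.8% | 81.7% |
| 0.0375 | 9.1% | 8.6% | 72.9% |
| 0.075 | 22% | 22% | 50.7% |

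**Power without the interviewees**

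Dropping 75 of 1,000 leaves 925, or 462.5 per group. Power = Φ(0.2 × √(462.5/2) − 1.96) = Φ(1.081) = 86.0%. If all 75 leave one group (425 against 500), the standard error is √(1/425 + 1/500) = 0.0660 and power is Φ(1.071) = 85.8%.

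**The case against.** Several stronger readings are tempting, and the documents do not support them.

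- **All 75 interviewees land in one arm.** The survey is confined to Weill Cornell, while interviewees come from several systems and can split between two telemedicine arms. Not every invitee will respond. Seventy-five is an upper bound at the planned interview number. This objection stands, and the smaller case belongs beside it.
- **Interviewees favour telemedicine.** The entry rule includes people who only attempted to use it, so some may have had failed attempts. The direction is unknown.
- **Provider nominations add to the bias.** Providers who nominate contented patients would raise satisfaction in every arm. The contrast moves only if the share or effect of nominees differs by arm, and no text says that it does. Nominations could add to the interviewee effect, offset it or do nothing. The two routes also overlap, because some interviewees are themselves provider-nominated.
- **The consent list is the unbiased sample.** It is opt-in and the survey is delivered through the patient portal. The section on heterogeneous treatment effects itself cites lower digital health literacy in older adults and racial differences in inpatient-portal use. The added routes may reach people whom the list misses, so removing every added route from the main analysis is not clearly an improvement.
- **The 0.2 SD margin is the study's test.** It applies only if a non-inferiority framework is adopted; the stated overall hypothesis is nondirectional. I use the margin as a yardstick.

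What remains is narrower. The interviewee route is tied to arm by its entry rules, and the plan neither limits its effect nor examines it.

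**Conclusion.** The concern holds as an uncontrolled, arm-related selection risk in the PRO contrast of the telemedicine arms with in-person-only care. It is not a demonstrated bias.

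Under the assumed 0.25 to 0.5 SD difference and 500 per arm, the shift is about 0.01 to 0.02 SD if a quarter of interviewees are Weill Cornell patients, which is minor. It reaches 0.04 to 0.08 SD at the upper bound, which is enough to raise a 5% type I error to between 9% and 22%. The bound rises if the interview sample is enlarged. For provider nominees the documents support only a recommendation to check: their number is open and a difference by arm is not shown.

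**What to change.** Before survey invitations go out, when route is easiest to capture:

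1. Record the recruitment route for each respondent, with separate flags for Aim 1B participation and provider nomination because the two overlap.
2. Exclude Aim 1B interviewees from the main PRO arm comparison. Use them for descriptive telemedicine-usability results, which the plan already restricts to people who accessed a telemedicine visit.
3. Report respondents by route and arm.
4. Run two sensitivity analyses of the arm comparison: one that also excludes provider nominees, and one that includes all respondents.

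The cost is one data field (two flags), some plan wording, a little more analysis and, at the planned interview number, at most 75 fewer respondents in the main comparison. If they are not replaced, two-group power at 0.2 SD falls from 88.5% to about 86%. The precision lost in the analysis without nominees cannot be computed, because their number is not given.

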The study, which brings together an experienced multidisciplinary team with expertise in telemedicine research, leverages the PCORnet National Patient-Centered Clinical Research Network (CRN) infrastructure through a collaboration among three CRNs and two health plans representing diverse urban and rural populations. Our aims are:

Aim 1: What are the features of primary care telemedicine programs newly implemented or expanded in response to the COVID-19 pandemic, and how is telemedicine offered to and experienced by diverse populations? In Aim 1A, we will conduct a comprehensive landscape survey of primary care leaders nationally, using a theory-informed survey instrument. Aim 1A will address an important knowledge gap on the extent and characteristics of telemedicine implementation during the COVID-19 pandemic. It will also provide crucial stakeholder-informed data about participating sites to support Aim 2. In Aim 1B, a qualitative study with patient and provider stakeholders will explore experiences with, barriers to, and facilitators of telemedicine and provide insights into disparities in delivery and use.

Aim 2: What is the comparative effectiveness of primary care telemedicine programs and capabilities on patient-centered outcomes and disparities in outcomes in chronic disease? In Aim 2A, we will apply natural experiment methods, leveraging CRN electronic health record (EHR) and claims data, to compare the effectiveness of (1) synchronous telemedicine alone; (2) telemedicine-supplemented in-person care; and (3) in-person care alone on patient-centered outcomes, including the quality of health care and the frequency of avoidable emergency department visits. In Aim 2B, we will examine how comparative effectiveness varies as a function of telemedicine program features (such as patient technical assistance and provider training). In Aim 2C, we will examine disparities in telemedicine use

PRINCIPAL INVESTIGATOR: [name]; [name]

and impact among patient subgroups, including socioeconomically vulnerable patient populations. Patient-reported outcomes include satisfaction with care and telemedicine usability.

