We propose a causal model informed by the Wagner Chronic Care Model in which productive disease management interactions between informed patients and prepared care teams are promoted by effective health systems as well as communities.³⁷ Critical relevant elements of the health system are processes to provide self-management support, design of the healthcare delivery system, and technologies such as clinical information systems and decision-support. In our causal model, for patients with chronic disease, access to care is a mediator in the causal pathway between the disruption in care from the pandemic and the outcomes in our study (e.g., unnecessary utilization such as unplanned ED visits, and satisfaction with care). To the extent that telemedicine improves access to care, it mediates this relationship. Furthermore, patient-provider communication is an additional mediator of this relationship, through its effect on self-management support as well as trust in the healthcare system.

However, one reason this study is important is that the abrupt nationwide transition makes it challenging to determine in advance whether telemedicine would be expected to have positive or negative impacts on care access and patient-provider communication, overall and within important patient subgroups. The pandemic prompted telemedicine use by patients who would otherwise not have been early adopters of telemedicine, increasing the diversity of patient users, including those from disadvantaged social circumstances or with older age who may encounter more barriers to successful use of telemedicine (stemming from limited device access, technology literacy, or broadband access, or primary language). These barriers would cause telemedicine to have a negative effect on care access and patient-provider communication, as well as patient satisfaction. Conversely, however, there are known instances in which people who would not have opted into the technology themselves nevertheless become effective users of the technology after being provided with an initial access experience.²⁶ Thus, the forced use of telemedicine may possibly have successfully promoted engagement with telemedicine and therefore improved access to care and patient-providers communication among some patients from less advantaged patient groups.

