Primary findings will be presented alongside descriptive statistics assessing the external and internal validity of the analysis, including balance across relevant covariates before and after matching. We will also use descriptive statistics to characterize the analysis population, identify sources of missingness in the data across outcomes and covariates as well as whether missingness may introduce selection bias into our analysis. In sensitivity analyses, we will multiply impute covariates for which there is meaningful evidence of missingness.

Heterogenous Treatment Effects

We hypothesize that patients in disadvantaged sociodemographic groups will derive less benefit from telemedicine than patients in majority groups because of barriers to use of telemedicine described in the conceptual model. We additionally hypothesize that more robust telemedicine programs (as defined in the Aim 1 taxonomy) will provide more benefit to patients than less robust ones.

We will explore variation in effects for the outcomes listed in Table 1 among pre-specified sociodemographic subgroups (race/ethnicity, rurality, median income for zip code) and clinical subgroups (COVID-19 patients vs. all other patients; low vs. high burden of illness; stable vs. unstable disease, as indicated by clinical measures of disease progression). Finally, we will use the Aim 1 survey for stratified analyses of telemedicine factors, such as historical use of telemedicine and patient technical assistance. Additionally, the Medicare data will allow us to conduct a subgroup analysis for our claims-based outcomes on dually eligible patients. Therefore, we will conduct eight separate subgroup analyses in all. We will use the same analytic approach described in the primary analysis to conduct these subgroup analyses and present the differences in treatment effect estimates with standard errors. We will also conduct univariate subgroup analyses with interaction effects to statistically test for differences in outcomes (as outlined below) among these subgroups.

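### Telemedicine usability (TUQ) is asked only of patients who accessed a visit, so Aim 2C usability comparisons are conditional on successful access and failed attempts go unrecorded

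*Combined protocol and SAP*

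**What the plan says.** Section E, Outcomes, describes a REDCap survey of 1,000 patients at one health system with two instruments. The first is PSQ-18, "which includes patient satisfaction, communication quality with providers, and accessibility/convenience of care", with no condition on telemedicine use. The second is conditional: "For individuals who accessed a telemedicine visit, we will ask questions adapted from the validated Telemedicine Usability Questionnaire (TUQ", with content "including the ease of use and access to the telemedicine service, quality of the interaction with the provider, and satisfaction". The word 'accessed' is not defined.

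Section B, at the end of the Aim 2C description, states: "Patient-reported outcomes include satisfaction with care and telemedicine usability". Table 1 has a single undivided row for patient-reported outcomes under the primary outcomes. Section F, Heterogenous Treatment Effects, explores Table 1 outcomes by race/ethnicity, rurality and area income, and gives the expectation: "We hypothesize that patients in disadvantaged sociodemographic groups will derive less benefit from telemedicine than patients in majority groups because of barriers". The causal model in Section F describes newly reached telemedicine users, "including those from disadvantaged social circumstances or with older age who may encounter more barriers to successful use of telemedicine", and adds: "These barriers would cause telemedicine to have a negative effect on care access and patient-provider communication, as well as patient satisfaction".

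For the Aim 1B interviews, Section C, Sample, uses a wider criterion: adult patients "with a chronic condition under study who have attempted to use or have used telemedicine". Section E allows these interviewees to be invited to the survey.

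**The concern.** Ease of use and access are part of what the TUQ items measure. Admitting only patients who got into a visit selects on the quantity being measured. A patient stopped by a missing device, poor broadband, language or unfamiliar technology would be expected to rate ease and access low, but is routed past those items. These are the barriers through which the plan expects disadvantaged groups to benefit less.

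What is at stake is narrow but real: what Aim 2C can conclude about disparities in usability. A small TUQ gap between subgroups could mean that usability is similar, or that patients for whom telemedicine was unusable were filtered out at different rates. With no failure item in the survey, the two cannot be told apart. An interviewee known from Aim 1B to have failed to connect could be enrolled in the survey and still skip the usability items.

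**Working it through.** **No plan figure to reproduce.** The documents give no sample size, power, effect size, standard deviation or failure rate for TUQ. The survey power statements in Section E, Power Calculation, concern satisfaction and do not bear on this point.

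**Does anything else capture failed attempts?**
- PSQ-18 is answered by failed attempters, but it rates care in general, not the telemedicine service.
- Aim 1B asks whether telemedicine succeeded, but in about 75 purposively sampled interviews, which cannot give failure rates by subgroup.
- The missing-data text in Section F plans imputation or likelihood methods for survey data and names nonresponse. It does not address a skip built into the questionnaire, and imputing from patients with access would carry the selection forward.

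**Direction.** Let A be the advantaged and B the disadvantaged group. Let f be the share of attempters who fail, and d the mean score among those with access minus the mean that failed attempters would give. Each group's mean over all attempters is its mean with access minus f × d, so

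(gap among all attempters) − (gap among those with access) = fB·dB − fA·dA.

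The disparity is understated only if fB·dB > fA·dA.

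**Illustration (all inputs assumed, 5-point score).** Means among those with access are 4.2 in A and 4.0 in B, so the observed gap is 0.20. Failed attempters would score the same in both groups, from 1.5 (dA = 2.7, dB = 2.5) to 3.5 (dA = 0.7, dB = 0.5). For example, with failure rates of 5% and 20% and a failure score of 1.5: 0.20 + 0.20 × 2.5 − 0.05 × 2.7 = 0.20 + 0.50 − 0.135 = 0.565.

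| Failure A / B | All-attempter gap, failures score 1.5 | All-attempter gap, failures score 3.5 | Observed 0.20 is |
|---|---|---|---|
| 5% / 10% | 0.315 | 0.215 | too small |
| 5% / 20% | 0.565 | 0.265 | too small |
| 10% / 30% | 0.68 | 0.28 | too small |
| 10% / 12% | 0.23 | 0.19 | about right |
| 10% / 10% | 0.18 | 0.18 | slightly too large |
| 15% / 10% | 0.045 | 0.145 | too large |

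With these means, understatement needs fB/fA above dA/dB, that is above 2.7/2.5 = 1.08 when failures score 1.5, or 0.7/0.5 = 1.40 when they score 3.5.

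**The case against.** The strongest reply is that the disparity the plan mainly expects is measured elsewhere. The causal model names care access, communication and satisfaction. These match the three PSQ-18 domains, and failed attempters answer PSQ-18. The overall hypothesis covers utilization and satisfaction, not usability. Usability among users is also a legitimate quantity if labelled as such. This stands, and it confines the point to TUQ. It does not supply a usability score or a failure rate for those who could not connect.

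Three stronger readings are tempting, and the documents do not support them.

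- *That the disparity is understated, and by a known amount.* If successful users in both groups score 4.2, failures score 1.5 to 2.0 and failure rates are 5% and 20%, the hidden gap is (0.20 − 0.05) × (4.2 − 2.0) = 0.33 up to 0.15 × 2.7 = 0.405. The zero observed gap there is built in by giving both groups 4.2. The 0.26-point effect in Power Calculation is a satisfaction difference between care programmes, so it is no benchmark for a usability gap. The plan also leaves direction open: the causal model allows that forced use helped some less advantaged patients, and the subgroup rationale cites evidence of possibly higher reported telemedicine use among Black patients.
- *That a three-arm TUQ test is planned and is spoiled by self-selection.* No section schedules one. The undivided row in Table 1 merely fails to exclude it, and the prose list of primary outcomes omits patient-reported outcomes.
- *That Aim 1B and the survey contradict each other.* An interview study and a user questionnaire may have different populations. The Aim 1B criterion matters only as a ready-made wording.

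It is also fair that the REDCap instrument is not shown and that 'accessed' could be read to include an incomplete visit. That is a reason to define the word.

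**Conclusion.** The point holds in a limited form. As written, TUQ is conditional on having accessed a visit, failed attempts contribute no usability score, and no described survey item counts them. Aim 2C usability comparisons therefore describe patients who got through, and the plan has no means of detecting or sizing the resulting selection.

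Understatement is the likely direction if failures are clearly more common in disadvantaged groups and would score low, as the plan's own barrier mechanism suggests. It is not established. In the illustration the observed gap is too small whenever group B fails at least twice as often as A, about right or slightly too large at similar rates, and too large if A fails more often. All those inputs are assumptions.

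PSQ-18, claims and EHR outcomes are untouched. This is a cheap improvement to one instrument, not a threat to the main comparison.

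**What to change.** - Define 'accessed', and branch the REDCap survey on having attempted or accessed a telemedicine visit, as Aim 1B already does.
- Add one item on whether the attempt succeeded.
- Give failed attempters the ease-of-use and access items, and report attempt-failure rates by subgroup beside the scores.
- Label the interaction-quality and satisfaction TUQ results as conditional on a completed visit.
- State in Table 1 that PSQ-18 is the between-arm patient-reported outcome, and that TUQ is reported descriptively and by subgroup among telemedicine attempters or users.

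The cost is one branching rule, one item, a wording change in Table 1, and different denominators across TUQ domains. One limit remains. The survey is delivered through the patient portal with emailed or texted links, so digitally excluded patients may be under-represented even with phone or mail invitations; failure rates among respondents may then be lower than among all attempters. If the survey has already been fielded, analysis cannot recover the skipped answers, and only the labelling and Table 1 changes remain available.
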